4.4.3 Analysis

- A summary of subjects included in each analysis set will be provided for Enrolled Set.
- By-subject listing including analysis set flag (Yes or No), and reason of exclusion from safety and PK set will be provided.

4.5 Demographic and Other Baseline Characteristics

The following summaries will be provided for demographic and other baseline characteristics based on Enrolled set.

- A summary of demographic variables and baseline characteristics:
Age (years), sex, ethnicity, height (cm), weight (kg), BMI (kg/m²).
$$\text{BMI (kg/m}^2\text{)} = \text{weight (kg)} / [\text{height (cm)}]^2$$
- A summary of other possibly relevant variables:
Alcohol consumption, tobacco consumption, caffeine consumption, and history of drugs.
- By-subject listings of demographic data and other baseline characteristics (as summarized above) will be provided.

Other lab tests performed during screening and baseline visits will also be listed:

- Serum virology and bacteriology at screening: Hepatitis B (HBs antigen), Hepatitis C (HCV antibodies), HIV 1/2 (HIV Ag/Ab combo), Treponema pallidum.
- Urine drug test at screening and Visit 2, day -1: cocaine, amphetamine, methamphetamine, cannabinoids (delta-9-tetrahydrocannabinol - THC), opiates
- Alcohol breath test.
- Serum pregnancy test at screening.
- Urine pregnancy test at Visit 2, day -1.

4.6 Medical and Surgical History

Medical and surgical history will be coded using the Medical Dictionary for Regulatory Activities (MedDRA version 22.0).

A summary of medical and surgical history by system organ class (SOC) and preferred term (PT) on Enrolled Set will be provided.

By-subject listings of medical and surgical history will also be provided.

4.7 Prior and Concomitant Medications/Procedures

Prior and Concomitant medications will be coded using the WHO Drug Dictionary Enhanced (WHODrug Global version March 2019).

Prior and Concomitant procedures will be coded using the Medical Dictionary for Regulatory Activities (MedDRA version 22.0).

Medications will be classified as “Prior” or “Concomitant” based on the comparison between start and stop dates of the medication and the date of first dose of study drug.

Medications that stop prior to the date of first dose of study drug will be classified as “Prior Medications”.

Medications that stop on or after the date of first dose of study drug will be classified as “Concomitant Medications”. Imputation of partial dates of medication records for classification of “prior” and “concomitant” is described in [Appendix 2](#).

Prior and concomitant procedures will be classified in the same way as medications.

- A summary of concomitant medications by ATC level 3 term and preferred name will be provided for Enrolled Set.
- A summary of concomitant procedures by SOC and PT will be provided for Safety Set.
- By-subject listing of concomitant medications and procedures will be provided.
- By-subject listing of prior medications and procedures will be provided.

4.8 Treatment Compliance

Exposure and compliance data will be summarized and listed based on Safety Set.

- A descriptive summary of treatment compliance variables will be provided:
 - Treatment duration (days) = last dose date – first dose date + 1
 - Total amount of exposure doses (ml)
 - Treatment compliance (%) = (total amount of actual dosage infused/total amount of prescribed dosage)*100
 - Treatment compliance by categories (<80%, 80%-120%, >120%)

Detailed IMP administration data and the treatment compliance variables will be listed.

Detailed standardized meals will also be listed.

4.9 Pharmacokinetics Analysis

4.9.1 Pharmacokinetic Concentrations

Pharmacokinetic plasma and urine concentration data for NAC will be listed by subject. Listings will include actual sampling times relative to dose administration, in addition the urine data listing will include the volume of urine collected, the concentration of NAC and the amount of NAC excreted per collection interval.

Plasma concentrations and urine amounts of NAC will be summarized descriptively. The following descriptive statistics will be presented for plasma and urine data obtained at each

nominal time point: n, arithmetic mean, SD, coefficient of variation (CV%), geometric mean, geometric SD, geometric CV% (calculated as: $gCV\% = \text{SQRT}(e^{s^2} - 1) * 100$; where s is the standard deviation of the log-transformed values), median, minimum and maximum values.

The following rules will be followed with regards to the number of decimal places and presentation of data in the tables and listings of concentration data:

- Source data shall be used in all derived PK concentrations without prior rounding
- The mean, standard deviation (SD), geometric mean and median will be tabulated to one more significant digit compared to the source data, but with a maximum of four significant digits.
- Minimum and maximum values will be tabulated to the same precision as the source data, but with a maximum of four significant digits.
- Geometric coefficient of variation (CV) % and coefficient of variation (CV%) will be presented to one decimal place.

The following descriptive pharmacokinetic graphs will be generated:

- Subject Profiles for NAC Plasma Concentration vs. Time Data for Single Dose – Linear Scale
- Subject Profiles for NAC Plasma Concentration vs. Time Data for Multiple Dose – Linear Scale
- Subject Profiles for NAC Plasma Concentration vs. Time Data for Single Dose – Semi-Logarithmic Scale
- Subject Profiles for NAC Plasma Concentration vs. Time Data for Multiple Dose – Semi- Logarithmic Scale
- Arithmetic Mean (\pm SD) NAC Plasma Concentration vs. Time Data for Single Dose – Linear Scale
- Arithmetic Mean (\pm SD) NAC Plasma Concentration vs. Time Data for Multiple Dose – Linear Scale
- Arithmetic Mean NAC Plasma Concentration vs. Time Data for Single Dose – Semi-Logarithmic Scale
- Arithmetic Mean NAC Plasma Concentration vs. Time Data for Multiple Dose – Semi-Logarithmic Scale
- Subject Profiles for Cumulative NAC Urine Amount Excreted vs. Time Data for Single Dose – Linear Scale
- Subject Profiles for Cumulative NAC Urine Amount Excreted vs. Time Data for Multiple Dose – Linear Scale
- Subject Profiles for Cumulative NAC Urine Amount Excreted vs. Time Data for Single Dose – Semi-Logarithmic Scale
- Subject Profiles for Cumulative NAC Urine Amount Excreted vs. Time Data for Multiple Dose – Semi-Logarithmic Scale

- Arithmetic Mean (\pm SD) Cumulative NAC Urine Amount Excreted vs. Time Data for Single Dose – Linear Scale
- Arithmetic Mean (\pm SD) Cumulative NAC Urine Amount Excreted vs. Time Data for Multiple Dose – Linear Scale
- Arithmetic Mean Cumulative NAC Urine Amount Excreted vs. Time Data for Single Dose – Semi-Logarithmic Scale
- Arithmetic Mean Cumulative NAC Urine Amount Excreted vs. Time Data for Multiple Dose – Semi-Logarithmic Scale

4.9.2 Handling of Values Below the Limit of Qualification (BQL)

For listings, all concentrations below the limit of quantification (BQL) will be labeled as “BQL” in the concentration data listings. Missing data will not be imputed.

For calculation of descriptive statistics of concentration by time point and graphs of arithmetic means, values that are BQL will be substituted with zero.

For calculation of geometric means, as a consequence of BQL values, calculated geometric means could be null. In the presence of any null values, the geometric mean will be reported as not calculated (NC).

4.9.3 Pharmacokinetic Parameters

Pharmacokinetic parameters will be listed by subject. Descriptive statistics for calculated PK parameters will include: n, arithmetic mean, SD, CV%, geometric mean, geometric CV%, median, minimum and maximum values. For t_{max} , only median, minimum and maximum values will be presented. No descriptive statistics will be determined when fewer than three individual PK parameters are available.

The following rules will be followed with regards to the number of decimal places and presentation of data in the tables and listings for PK parameters:

- Individual PK parameters will be presented to four significant digits, with the exception of t_{max} , which will be presented to two decimal places.
- Parameters derived directly from source data (e.g. C_{max}) shall be reported with the same precision as the source data (if this is not four significant digits).
- The mean, geometric mean, median and SD values will be reported to four significant digits except for CV% which will be presented to one decimal place.
- For t_{max} the minimum and maximum will be presented to two decimal places and all other descriptive statistics will be presented to three decimal places.
- Estimates and confidence intervals in the form of percentages will be presented to two decimal places.

After receiving Plasma and urine PK concentration data from Vendor, statistical outlier testing will be performed by using boxplots to identify outliers as described below:

- Q1: 25th percentiles; Q3: 75th percentiles; Interquartile Range (IQR) = Q3 – Q1;
- Lower Far outlier: value < Q1 – 3 × IQR;
- Upper Far outlier: value < Q3 + 3 × IQR.

The far outliers will be identified, reviewed and discussed during the Data Review Meeting prior to Database lock. Outliers that may have an impact on the concentration-time profiles will be discussed and it will be determined whether to exclude them from PK concentrations, PK parameters or PK set. As a general rule, outliers will be ruled out from tabulations but kept in data listings.

If a subject or outlier is required to be excluded from PK analysis, details will be documented in Data Review Meeting minutes, including an external excel file that documents the required Analysis Flag on applicable analysis datasets level.

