Brown *et al.* ([14](#)) investigated the PK of NAC infused i.v. to 24 healthy men at rest and during exercise. NAC was infused at the dose of 125 mg/kgxh for 15 min followed by 25 mg/kgxh for 35 min to healthy men at rest. Then, the infusion continued during exercise until fatigue. The authors found NAC peak concentrations in plasma at the end of the initial loading infusion. Mean peak concentration of total NAC was 205.1±68.3 mg/L, while mean CL was 0.164 L/kgxh.

It is worth noting that, while scientific literature shows that PK profiles of NAC after oral administration are very consistent (in terms of half-life, rate and extent of exposure, bioavailability, dose-linearity, etc.) among various publications, this is not the case for the data obtained after i.v. dosing. In fact, for this administration route, published studies differ in several key aspects, i.e., for example, type of administration, applied bioanalytical methods, drug doses, calculation methods for PK parameters. Furthermore, the number of subjects enrolled in each published study is very small. For these reasons, the comparability of the literature data is low among the published studies and potentially also to the expected results of the present study.

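### The far-outlier screen in SAP 4.9.3 names no scale or grouping; on raw concentrations at the quoted peak variability it almost never flags a low value

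*SAP*

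**What the plan says.** SAP 4.9.3 introduces the screen as follows: "After receiving Plasma and urine PK concentration data from Vendor, statistical outlier testing will be performed by using boxplots to identify outliers as described below". The quantities are defined as "Q1: 25th percentiles; Q3: 75th percentiles; Interquartile Range (IQR) = Q3 – Q1", and the fences as "Lower Far outlier: value < Q1 – 3 × IQR" and "Upper Far outlier: value < Q3 + 3 × IQR". No transformation is mentioned. Nor does the SAP say whether quartiles are taken at each nominal time or over pooled values.

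Flagged values go to the Data Review Meeting before database lock, where "it will be determined whether to exclude them from PK concentrations, PK parameters or PK set". The default is also stated: "As a general rule, outliers will be ruled out from tabulations but kept in data listings".

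The same concentrations are summarised in SAP 4.9.1 with a geometric mean, geometric SD and geometric CV%, "where s is the standard deviation of the log-transformed values". For urine, that section summarises amounts, although the screen in 4.9.3 names concentrations. SAP 4.9.2 replaces BQL values by zero in the arithmetic concentration summaries.

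**The concern.** Drug concentrations cannot be negative and are usually right-skewed, and the SAP's own geometric statistics treat them on the log scale. A symmetric 3×IQR fence on the raw scale is not symmetric in effect for such data. The lower fence can sit below zero, where no value can reach it, while the upper fence stays within reach of genuine high values.

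Two things are at stake. With removal from tables as the default, the tables would tend to lose high values and not low ones, which narrows the reported SD and CV%. In a purely descriptive study those are deliverables. The screen would also have little power against low-side errors such as a swapped tube or a spurious zero.

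Urine adds a separate difficulty. Concentration depends on urine volume, and Protocol 11.2 lets subjects drink water as they wish. A small concentrated void can therefore be flagged although the amount of NAC excreted is ordinary.

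**Working it through.** The documents give no operating figure for this screen, so there is none to reproduce. N = 24 is stated not to come from a calculation (SAP 4.11).

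**Step 1: the sign.** Taken literally, the printed upper rule flags about 99% of values. It is read below as greater-than.

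**Step 2: when the lower fence reaches zero.** Q1 − 3(Q3 − Q1) = 4Q1 − 3Q3.
- Normal: the quartiles are mean ∓ 0.6745 SD, so the fence is mean − 7 × 0.6745 SD = mean − 4.721 SD. It is zero at CV = 1/4.721 = 21.2%.
- Lognormal with log-SD s: zero when Q3/Q1 = exp(1.349 s) = 4/3, so s = 0.2877/1.349 = 0.2133 and CV = √(exp(0.2133²) − 1) = 21.6%.

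**Step 3: the spreads quoted in Protocol 6.2** (normal form).

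| Quantity | Mean ± SD | CV | Lower fence |
|---|---|---|---|
| Peak, total NAC (mg/L) | 205.1 ± 68.3 | 33% | 205.1 − 322.4 = −117 |
| Cmax, free NAC (µmol/L) | 16.0 ± 7.9 | 49% | 16.0 − 37.3 = −21.3 |
| AUC, total NAC (mg/L×h) | 93.9 ± 9.6 | 10% | 48.6 |
| Vdss (L) | 17.4 ± 2.8 | 16% | 4.2 |
| Half-life, total NAC (h) | 2.6 ± 0.3 | 12% | 1.18 |

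A third Cmax is given as median 121 µM with range 82.9–162 (N = 6). Assuming normality, SD ≈ 79.1/2.534 = 31.2, so the CV is about 26% and the fence about −26. The last three rows of the table are parameters, which this rule does not test, but they bear on how variable the concentrations may be.

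**Step 4: samples of 24.** Simulated lognormal values with fences from sample quartiles. The SAP names no percentile definition, so two were tried: linear interpolation, and the (n+1)p rule.

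| | CV 33% | CV 49% |
|---|---|---|
| Lower fence ≤ 0 | 91–96% | 99.4–99.8% |
| At least one clean value flagged high | 6–10% | 13–19% |
| At least one clean value flagged low | < 0.02% | < 0.01% |
| Same, log scale, each side | 0.3–0.9% | 0.3–0.9% |

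The figures of 10% and 18–19% belong to linear interpolation. With that definition the lower fence is essentially never ≤ 0 at CV 10%, and is ≤ 0 in about 4% of samples at CV 16%.

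**Step 5: effect on the tables if every flag were deleted** (linear interpolation). The mean falls 0.6% at CV 33% and 1.8% at CV 49%. The SD falls 3.5% and about 8%. At CV 10–16% the mean falls by less than 0.1%.

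**Step 6: detecting a low-side error.** One of 24 values is divided by ten at CV 33%. The raw fence catches it about 3% of the time and the log fence about 94% (1% and 88% under the other percentile definition). The reason is visible in the log fences. With s = √ln(1 + 0.333²) = 0.324, they lie a factor exp(4.721 × 0.324) = 4.6 from the median, at about 42 and 900 mg/L for the 205.1 ± 68.3 figures. At CV 49% the factor is exp(4.721 × 0.467) = 9.1, so a ten-fold error is only just outside and log-scale detection falls to about half. It is still far above the raw scale, which catches under 1%.

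**The case against.** **Choice of inputs.** The 33% CV comes from a weight-based 15-minute loading infusion, and the 49% CV is for free NAC, whereas this trial assays total NAC. Protocol 6.2 itself warns of low comparability. The study closest in analyte and dosing quotes CVs of 10–16%, though for parameters. A one-compartment illustration from those figures (independent normal parameters assumed) keeps the lower fence positive to about 4–8 h and makes it negative from about 6–10 h. This stands. A reader might infer that only high values can ever be flagged, and the documents do not support that.

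**Not every draw behaves like a peak.** Pre-dose samples on Day 1 and Day 4 should be mostly BQL. Adding up expected flags over all 36 plasma time points would therefore mislead, and only rates per time point are used here.

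**Flagging is not deletion.** The Data Review Meeting decides, decisions are minuted, and values stay in the listings. This also stands, although the meeting starts from what the fences flag and the stated default is removal from tables.

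**Other safeguards.** It is tempting to conclude that low-side errors go undetected. They need not. SAP 4.8 compares infused with prescribed dose, SAP 4.4.2 lists administration errors as grounds for exclusion from the PK set, SAP 4.3.2 covers protocol deviations, and SAP 4.9.1 plots every subject's profile on linear and semi-logarithmic axes.

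**Silence on scale.** The SAP does not say raw. But a rule written in terms of the value, with no transformation, will most naturally be programmed that way.

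**Conclusion.** The concern holds in a limited form. If SAP 4.9.3 is applied to raw concentrations by nominal time with the upper sign corrected, the screen is close to one-sided wherever the CV is well above 21–22%. The quoted peak-concentration spreads are in that range. At CVs of 10–16% the lower fence is usually positive, so one-sidedness is not a property of the whole profile.

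The effect on tabulated means is minor (at most about 1.8%). It is larger on the SD (up to about 8%), and both figures assume that the meeting removes every flagged value. The more important weakness is that this particular screen would miss most low-side errors at peak-type variability. Dose records, deviation review and individual profiles cover part of that gap.

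The figures assume lognormal values, 24 subjects per time point and quartiles by nominal time. The urine point rests on reasoning and has not been quantified.

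**What to change.** In SAP 4.9.3:
- Correct the upper rule to greater-than.
- Apply the 3×IQR fences to log-transformed concentrations at each nominal time point.
- List zero and BQL values that occur before a subject's last measurable concentration, and review them separately.
- For urine, screen Ae(t1-t2), the amount excreted per collection interval, which is what SAP 4.9.1 summarises.

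The cost is about a sentence of text, a small programming change and one extra listing. The drawback is that zeros have no logarithm, so the separate BQL review is a necessary part of the change.

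The revision history shows that the database is already locked. SAP section 1 provides an addendum for changes after lock. The log-scale screen should be reported there as post hoc, stating which values were flagged and removed under the rule as run and whether the log-scale rule would have differed.

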6.2 Clinical pharmacology and pharmacokinetics

Several pharmacokinetic (PK) studies were carried out in healthy volunteers (4, 5, 6, 7, 8, 9, 10, 11, 12, 13, 14). Further PK studies were carried out in patients with chronic liver damage (15), with liver damage caused by paracetamol overdosage (16), in subjects under long-term treatment for chemoprevention (17), in patients with respiratory disorders (18) and in patients with End Stage Renal Diseases (19).

In the clinical studies, NAC was administered orally and intravenously both as single and repeated doses. Oral NAC was administered in different dosage forms, such as capsules, granulate, effervescent tablets, fast dissolving tablets, slow-release tablets.

In particular, Borgström *et al.* (4) studied for the first time the PK profile of NAC after i.v. dose of 600 mg of NAC infused over 5 min in 10 healthy male and female volunteers in comparison with 3 other oral dosage forms. The PK parameters obtained by the authors after i.v. infusion are summarised in the following table.

Table 6.2.1 PK parameters of plasma free NAC (N=10)

C_{max} (μmol/L)	t_{max} (h)	CL (L/kgxh)	CL_r (L/kgxh)	t_{1/2} (h)	A_{e0-12} (% of dose)
16.0 \pm 7.9	0.65 \pm 0.33	0.207 \pm 0.017	0.058 \pm 0.011	2.27 \pm 0.32	29.0 \pm 3.2*

*mean \pm SD is reported; *: N=9; Source: 4*

However, the authors analysed NAC in deproteinised plasma thus missing the protein-bound NAC in their measurements.

Olsson *et al.* (5) improved the bioanalytical method and were able to measure the total NAC by reduction of the disulphide bonds in plasma before precipitating proteins. After single i.v. dose of 200 mg of NAC to 6 healthy volunteers, the authors found the following PK parameters:

Table 6.2.2 PK parameters of plasma total NAC (N=6)

	C_{max} (μ M)	V_{ss} (L/kg)	CL (L/kgxh)
T	121 (82.9 – 162)	0.47 (0.46 – 0.55)	0.11 (0.09 – 1.13)

median (range) is reported; Source: [5](#)

Jones *et al.* ([15](#)) studied the bioavailability of NAC after single i.v. dose of 600 mg of NAC infused over 3 min to patients with chronic liver disease, but also to 6 healthy male and female volunteers as control subjects. The authors found the following PK parameters for total NAC:

Table 6.2.3 PK parameters of plasma total NAC (N=6)

AUC (mg/Lxh)	CL _r (L/h)	$t_{1/2}$ (h)	Vd_{ss} (L)
93.9±9.6	6.5±0.8	2.6±0.3	17.4±2.8

mean±SD is reported; Source: [15](#)

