CL _t :	Total body clearance, calculated, if feasible, as Dose/ AUC _(0-∞)
V _{ur} :	Measured overall volume of urine collected during each collection interval.
Ae _(t1-t2) :	Amount excreted in the urine at each interval collection
Ae _(0-tz) :	Cumulative amount excreted up to tz hours, where tz is 4, 8, 12, 24 or 32 will be calculated as the sum of the products of concentration and urine volume over the appropriate collection intervals
Ae _(0-t) :	Total amount of NAC excreted in urine from single dose up to 32 h
Fe _(0-tz) :	The fraction of unchanged drug excreted in urine will be calculated as fe=Ae/Dose, up to tz hours, where tz is 4, 8, 12, 24 or 32 hours
Fe _(0-t) :	Total fraction of NAC dose excreted in urine from single dose up to 32 h
CL _r :	Renal clearance, calculated, if feasible, as Ae _(0-t) / AUC _(0-∞)

The following PK parameters will be measured and/or calculated for plasma NAC, after multiple doses of IMP:

C _{ss_max} :	Maximum NAC plasma concentration at steady-state will be obtained directly from the concentration data
t _{ss_max} :	Time to achieve C _{ss_max}
C _{ss_min} :	Trough NAC plasma concentration at steady-state, measured as the concentration at t=12 h
AUC _{ss(0-t)} :	Area under the concentration-time curve at steady-state from the last multiple dose to the last observed concentration time t, calculated with the linear up/log down trapezoidal method

AUC _{ss(0-12)} :	Area under the concentration-time curve at steady-state in the tau interval (from the last multiple dose to 12 h post-dose), calculated with the linear up/log down trapezoidal method
C _{ss_av} :	Average NAC plasma concentration at steady-state, calculated as AUC _{ss(0-12)} /tau
R:	Accumulation ratio, calculated as AUC _{ss(0-12)} / AUC ₍₀₋₁₂₎
A _{ess(0-t)} :	Total amount of NAC excreted in urine from the last multiple dose to 32 h at steady-state
DF%:	Degree of fluctuation over one dosing interval at steady-state, calculated as (C _{ss_max} - C _{ss_min}) / C _{ss_av} *100

The sampling schedule is considered adequate if the ratio AUC_(0-t) / AUC_(0-∞) equals or exceeds a factor of 0.8 (i.e. if %AUC_{extra} is <20%) for more than 80% of the individual PK profiles. This assures that the primary variable AUC_(0-t) covers a sufficient percentage of the theoretical total extent of exposure.

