4.4.2 Reasons for exclusion from the PK set before statistical analysis

Reasons for the exclusion of subjects from the PK set are the following:

- intake of concomitant medications which could render the plasma concentration-time profile unreliable
- Adverse events (AEs) which could render the plasma concentration-time profile unreliable
- administration errors which could render the plasma concentration-time profile unreliable
- other events which could render the plasma concentration-time profile unreliable

If one of these events occurs, it will be noted in the Case report form (CRF) during the study.

The samples from the subjects excluded from the PK set should still be assayed and the results listed. Subjects should not be excluded from the PK set if the AUC_{0-t} covers less than 80% of the $AUC_{0-\infty}$.

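### SAP 4.9.3 removes far-outlying concentrations from the tables by default, with no cause required and no summary that keeps them; where genuine high values go, SD, CV% and maximum come out too small

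*SAP*

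**What the plan says.** The screen is in SAP 4.9.3: "After receiving Plasma and urine PK concentration data from Vendor, statistical outlier testing will be performed by using boxplots to identify outliers". Far outliers lie more than three interquartile ranges beyond the quartiles. They are reviewed at the Data Review Meeting before lock, where "it will be determined whether to exclude them from PK concentrations, PK parameters or PK set". The default follows: "As a general rule, outliers will be ruled out from tabulations but kept in data listings". Exclusions are recorded in the minutes and in analysis flags.

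The upper limit is given as "Upper Far outlier: value < Q3 + 3 × IQR". The scale of the test (raw or log) and its grouping (time point, period) are not stated.

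The tables concerned are those of SAP 4.9.1, which report at each "nominal time point: n, arithmetic mean, SD, coefficient of variation (CV%), geometric mean, geometric SD" and further statistics including the maximum, and the parameter tables of SAP 4.9.3. One primary variable is a single tested concentration. SAP 3.2.1 defines Css_min as "Trough NAC plasma concentration at steady-state, measured as the concentration at t=12 h".

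The exclusion reasons in SAP 4.4.2 and Protocol 15.1.2 concern events, for example "administration errors which could render the plasma concentration-time profile unreliable". Neither section contains a rule based on the size of a value.

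**The concern.** Being extreme is not evidence of error. The only trigger named for discussing exclusion is a possible impact on the concentration-time profile, which describes influence. The plan is more lenient with known defects: Protocol 12.3.1 does not automatically exclude a subject for a confirmed out-of-window sample, and Protocol 15.1.2 keeps subjects whose AUC(0-t) covers less than 80% of AUC(0-∞).

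Concentrations are usually right-skewed. A symmetric fence on the raw scale then flags almost only high values. If these are genuine and the default is followed, the tables understate the between-subject spread and the upper range of exposure. A reduced n and the listings would show that something was removed, but not what the summary would have been.

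**Working it through.** The plan has no figure to reproduce, because SAP 4.11 states that the sample size was not calculated. The check asks what the rule does when every value is genuine and every flag leads to removal.

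**Inputs**
- n = 24 (SAP 4.11). Fences at Q1 − 3×IQR and Q3 + 3×IQR (SAP 4.9.3), with the upper one read as *greater than*. Results are ranges over two quartile definitions (SAS PCTLDEF=5 and linear interpolation).
- CVs are assumed. Reference values from Protocol 6.2:
  - V in Table 6.2.3 (600 mg over 3 min, six healthy controls): 2.8/17.4 = 16.1%
  - half-life in the same table: 0.3/2.6 = 11.5%
  - peak total NAC in the study of infusion at rest and during exercise: 68.3/205.1 = 33.3%
  - free-NAC Cmax in Table 6.2.1: 7.9/16.0 = 49.4%
- The 22% case is V with a 15% residual: √(0.161² + 0.15²) = 0.220.

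**Step 1: one table of 24 lognormal values, raw scale (200,000 simulated sets)**

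| CV | sets with at least one flag | average CV%, kept → removed |
|---|---|---|
| 16% | 2.3-3.5% | 15.8 → 15.6-15.7 |
| 22% | 3.6-5.1% | 21.7 → about 21.4 |
| 33% | 7.6-9.6% | 32.3 → 31.3 |
| 49% | 15.3-18.5% | 47.3 → 44.4 |

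The last two averages come from a separate run of 100,000 sets at CV 33% and 49% with linear-interpolation quartiles.

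**Step 2: tables with a flag.** SD falls 26-35%, the maximum 17-37% and the mean 2-10%; 96-100% of flags are high. Against the true SD, the SD with all values kept is 8-20% too large in these selected tables, and the SD after removal is 20-24% too small.

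**Step 3: by plasma time point.** One compartment, 600 mg over 5 min, V = 17.4±2.8 L and half-life = 2.6±0.3 h drawn independently as lognormals, residual CV 5% or 15% independent across times, 10,000 trials.
- k = ln 2/2.6 = 0.267 per h. C(12 h) ≈ (600/17.4) × exp(−0.267 × 12) = 34.5 × 0.041 ≈ 1.4 mg/L, far above the 10 ng/mL quantification limit, so values below that limit play no part.
- At 5 min: √(0.161² + 0.05²) = 0.17, or 0.22 with the 15% residual, so CV is 17-22%. A flag occurs in 2.5-5.6% of sets.
- At 12 h the log-scale SD is about √(0.16² + (12k × 0.115)² + residual²), with 12k × 0.115 = 3.20 × 0.115 = 0.368. This gives CV of about 42-45%. The simulation after the last dose gives 41-44%, with a flag in 8-12% of trials. When that happens to Css_min, SD falls 31-33%, the maximum 32-35% and the mean about 8%.
- Over 14 post-dose times up to 12 h × 2 occasions = 28 tables, 0.9-1.8 are affected on average. At least one is affected in 27-35% of trials (residual 5%) or 61-72% (residual 15%).
- Using AUC (93.9±9.6 mg/L×h) with V in place of half-life: CV at 12 h is 67-69%, with a flag in 13-18% after the last dose. At least one table is affected in 30-39% or 60-71% of trials.

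**Step 4: log scale.** Only 0.9-1.6% of sets have a flag, and about half of those flags are high. The one-sidedness comes from using a symmetric fence on skewed raw data.

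**Step 5: the inequality taken literally.** It would flag 99.8% of values at CV 20% and 99.1% at CV 49%, so it cannot be what was meant.

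**The case against.** **The meeting decides.** Far outliers are reviewed case by case before lock, and the general-rule sentence can be read as saying only where already excluded values are displayed. Removal is indeed not automatic, and retention would lower every figure above. But the SAP gives no criterion for keeping a value, and the values are known when the decision is made. If display is all that is meant, the sentence should say so.

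**Other sections report exclusions.** SAP 4.3.2 refers to a Protocol Deviation Specification, not available here, and plans a summary of PK-set exclusions by reason; SAP 4.4.3 lists the reasons. That covers removal of a subject from the PK set. It does not supply the SD, CV% or maximum without removal, and nothing in the SAP shows that it sets a cause criterion for single values.

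**The comparator is inflated.** Tables chosen because they contain an extreme value have an SD above the truth, as step 2 shows. This stands, and it reduces the understatement of the true SD to 20-24%. The direction does not change.

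**The model is thin.** It rests on SDs from six subjects and an assumed residual. With no residual, at least one table is affected in only 13-18% of trials. Protocol 6.2 itself warns that the intravenous literature is poorly comparable, possibly also with this study. The per-trial figures are therefore illustrative.

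**The reversed sign may come from the text conversion.** SAP Appendix 3 shows the same sign where multiplication must be meant. The point should be checked against the PDF.

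**Timing.** SAP 4.0 followed database lock, so rewording cannot change how the meeting was run. This affects the route, not the point.

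**Conclusion.** The concern holds. Removal is the stated default, no cause is required, and no summary with the values kept is planned. The change should be made, with medium confidence in the size of the effect.

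The effect is conditional. Most tables would have no flag, and at CV 16-22% the average table barely changes. Where a genuine high value is removed, the reported SD is about a quarter to a third below the SD with all values kept. Css_min is among the more exposed variables, with a flag in 8-12% of trials under the Table 6.2.3 inputs. These sizes assume lognormal data, testing by time point on the raw scale, genuine values throughout and removal of every flag.

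**What to change.** Correct the upper fence to value > Q3 + 3×IQR. Replace the general-rule sentence with, for example:

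> Far outliers are flagged and discussed but remain in all PK summaries and in the PK set unless a cause is documented independently of the value: a reason listed in SAP 4.4.2, or a documented sampling or bioanalytical error. A sensitivity summary without the flagged values is provided.

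The requirement for an independently documented cause matters, because SAP 4.4.2 concerns whole subjects and includes an open-ended category of other events. State also the scale and grouping of the test, for example by nominal time point and period.

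Because the database is locked, the route is the SAP Addendum foreseen in SAP section 1. If values were excluded, it should add the summaries with those values kept.

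The cost is wording and one sensitivity summary, covering each plasma, urine and parameter table with a flagged value. Reported SD and CV% may be somewhat larger, and a true error with no documented cause would stay in the main table, although the sensitivity summary would expose it.
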